The pilot impact evaluation will consist of a blocked partially nested randomised control trial design. 47 blocks of up to 20 CYP between the ages of 8 and 17 years old will be randomised using split randomisation (we expect most blocks to consist of 16 CYP, with an extra 4 spots for oversubscription). Each block will be split into two groups, with 8-10 CYP randomised to a treatment group which receives access to WeMatter's support services, and 8-10 CYP to a waitlist control group where they will receive WeMatter after the treatment group have completed the service CYP will be recruited for the randomised trial from referrals to Victim Support from all areas in England. The blocks of CYP will be organised according to age group and their preference for the setting in which sessions are delivered (home- or school-based). For the treatment group, CYP mental wellbeing will be measured using the Stirling Children's Wellbeing Scale and collected by Victim Support's trained professionals during one-to-one Zoom calls with the CYP before and after the support sessions. Outcome data will be collected at the same timepoints (both pre-intervention) for the control waitlist group.

Implementation and process evaluation

We will use a combination of administrative service data and interviews with WeMatter facilitators, CYP beneficiaries, and their non-abuser parents/carers. We will interview CYP and their parents/carers across a range of demographic characteristics, from both treatment and control groups, to get rich insights into how they experienced the trial and the impact of the implementation of the intervention.

Iterative testing approach

We will conduct two reviews with Victim Support and Foundations during which Victim Support will provide feedback about the research design and the evaluation team will review the progress of the evaluation. At these meetings, we will consider changing elements of the research processes or design, to address any issues that arise during the pilot. This may include, for example, introducing additional outcome measures or approaches that may encourage CYP to participate in the trial and limit attrition (such as financial incentives), or changing who administers the outcome measures (known vs unknown facilitators).

Cost evaluation

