The pilot IE will consist of a blocked, partially nested, waitlist randomised control trial design. A partially nested randomised control trial refers to trials where participants in the treatment group receive intervention services in groups, causing clustering of outcomes, but where this same clustering does not occur for those in the control group (Lohr et al., 2014). Participating CYP will be organised into blocks of 20 CYP each consisting of a control and an intervention group of equal sizes and matched for age and programme delivery setting. The CYP within each block will be randomised between an intervention group that receives access to WeMatter’s group-based support services and a no-intervention waitlist control group. Those CYP randomised to the waitlist (control group) will receive access to WeMatter following the completion of the treatment groups’ initial programme of support sessions (so after ~10 weeks).

The trial will run WeMatter groups across a 43-week period. The delivery setting and number of groups have been pre-planned based on Victim Support’s estimated number of referrals and demand. The age group will be determined by demand and, once a block of 20 CYP has formed, an age-specific group will be arranged for the next available start date given the groups preferred delivery setting. Victim Support will review the number of referrals during the delivery period and adjust the delivery plan accordingly. If needed, Victim Support will also implement targeted communications to encourage referrals.

Table 2 has a summary of the trial design and Figure 1 provides an illustration of the evaluation process, including the consent process and data collection points.

Table 2: Summary of pilot impact evaluation trial design

[figure not shown]
Trial type and number of arms		Two-arm blocked partially nested randomised controlled trial, with individuals randomised to a treatment or waitlist control group.
Unit of randomisation		Individual
Stratification variables (if applicable)		The sample is stratified by age group (8–12, 13–15, and 16–17) and individuals’ preference for the setting of delivery of the sessions (home- or school-based).
Primary outcome	Variable	Mental Wellbeing

	measure (instrument, scale)	Stirling Children's Wellbeing Scale (12-item questionnaire, each item a Likert scale from 1-5, resulting in aggregated scores between 12 and 60) Collected in Week 1 and Week 10.

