In the specifications in Table 3, the study sample size was previously determined by the resources and funding available to deliver the WeMatter service for this pilot evaluation. Our estimates are based on the trial including 47 blocks, with 16 CYP included in each block, the same number of WeMatter groups and control groups, and each group consisting of eight CYP. This equates to a total study sample of 752 CYP, 376 in the treatment group and 376 assigned to the waitlist control group. The different specifications in the table reflect that there is a very high degree of uncertainty about several aspects of the trial design. This includes a high degree of uncertainty about the level of clustering of outcomes we should expect within the treatment group in each block, and the likely correlation between the Week 1 and Week 10 outcome measures, particularly since the outcome measure will also be applied to an older age group it is not validated for. The degree of variability in the treatment effects across blocks is also unknown.

Reflecting the uncertainties about key aspects of the design, Table 3 reports different specifications of our estimates based on reasonable lower and upper range values we expect to observe within social experiments given the type of primary outcome included in this evaluation. For the intraclass correlation (ICC), which is a measure of the extent of outcome clustering (or the correlation in outcomes among participants within each group in a block), we report estimates assuming an ICC of between 0.01 and 0.15. We provide estimates assuming the proportion of variance in the outcome explained by control variables, such as the initial measure of the outcome, is between 0.3 and 0.7. We also report specifications according to different degrees of variability in the standardised treatment effects across blocks, assuming values between 0 and 0.5.

Description of MDES calculation results

The results in Table 3 show that assuming a scenario with low levels of clustering (0.01), where control variables explain a relatively low levels of the variance in the outcome (0.3), and no variability in the treatment effects across blocks, the trial is powered to detect an effect of 0.17, or larger (Column A). A more optimistic scenario where the control variables explain a higher degree of the variance in the outcome (0.7) would improve the precision of the trial, providing a smaller MDES of 0.11 (Column B).

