$$y_{ijh} = \beta_0 + \beta_1 T_{ijh} + \beta_2 X_{ijh} + \theta_{jh} T_{ijh} + \gamma_{ih}(1 - T_{ih}) + \varepsilon_{ijh} T_{ijh}$$

We define y as the aggregate score of the Stirling Children's Wellbeing Scale collected in Week 10, i as the indicator for individual participants, j as the cluster indicator, and h as the block indicator. The clusters refer to the WeMatter groups so participants in the same WeMatter group will belong to the same cluster. T is the treatment variable (0 = control group, 1 = treatment group) and X is a vector of control variables (including only the outcome measure collected in Week 1 in the parsimonious specifications). The parameter β_0 is an intercept, β_1 is the treatment effect and β_2 is a vector of the coefficients of the control variables. The error terms $\theta_{jh} \sim N(0, \sigma_\theta^2)$, $\gamma_{ih} \sim N(0, \sigma_\gamma^2)$, and $\varepsilon_{ijh} \sim N(0, \sigma_\varepsilon^2)$ are respectively the random effects representing the between cluster variation in the treatment group, the individual variation in the control group, and the individual variation in the treatment group. A simple explanation for the intuition underpinning this estimation approach is that it estimates the overall effect of the treatment by averaging the H separate block treatment effects. In essence, we have H independent replications of a basic partially nested randomised controlled trial (each block represents a basic partially nested randomised controlled trial), and the approach averages their results to estimate WeMatter's treatment effect (Lohr et al., 2014).

We will report the estimated coefficients, standard errors, 95% confidence intervals and report the effect size of the intervention in both the absolute terms and as a proportion of the standard deviation in the control group (Glass's Delta). The standard threshold of 0.05 will be used to determine statistical significance, and we will not adjust for multiple hypotheses (following Foundations' requirements in their statistical guidance).

Secondary analysis

Secondary outcome

The effects of WeMatter on any secondary outcome(s) agreed in July 2024 will be estimated using the same model described above for the primary analysis.

⁷ Where there is missing outcome data for some trial participants, we will perform a modified intention-to-treat analysis discussed below.

Subgroup effects

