Additional specifications of the regression model will consider further regression adjustments, for example, controlling for imbalances in baseline characteristics (collected by Victim Support during the referral and triage stage) such as year of birth, gender, sex at birth, public care status e.g. looked after child or care leaver, disability/additional needs, ethnicity, English as Alternative Language (EAL), free school meal status, source of referral, other needs captured by Victim Support systems (Lin, 2013). We will also examine more conservative estimators that include block fixed effects in the regression specification as a robustness test and include interaction terms between the treatment and blocks, allowing treatment effects to vary between blocks (Lohr et al., 2014).

Sensitivity analysis

We will also perform a sensitivity analysis, excluding any sibling groups, in case this relationship between evaluation participants affects their outcomes.

Missing data

If there is missing data, we will need to consider the likely reason for this missingness. In line with the statistical guidance from Foundations, the full sample baseline characteristics, the baseline characteristics of those lost to follow up, and the baseline of those analysed will be reported in a table side by side.

If the levels of missingness and differential attrition are low, then we can reasonably estimate the ITT, or more precisely a modified ITT where we include all participants that we have outcome data in the analysis according to their randomised group (treatment or control). We will also report estimates for a complete-case analysis where missing data varies according to outcome, which will indicate estimates using a common sample across outcomes.

However, a key threat to the validity of a randomised trial is attrition and missing participant outcome data. These issues can severely impact the reported estimates' risk of bias. There are several measures in place to minimise the issue of missing outcome data:

- When a CYP in the treatment group indicates they would like to stop attending the WeMatter programme, the facilitator will ask if they would still be happy to arrange a follow-up call to check in and ask them a few questions on their mental wellbeing as in the initial one-to-one call.
- If a CYP does not attend the final group session, the facilitator will try to get in touch with the CYP to encourage them to still attend the concluding one-to-one call.

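### The treatment-by-block robustness model is called more conservative, but with one WeMatter group per block its model-based standard error leaves out the between-group variance

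*Protocol*

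**What the plan says.** The Summary (Pilot impact evaluation) states that "Each block will be split into two groups", one for treatment and one for the waitlist. The Design section describes "blocks of 20 CYP each consisting of a control and an intervention group of equal sizes". The MDES section counts on "the trial including 47 blocks, with 16 CYP included in each block, the same number of WeMatter groups and control groups", giving "376 in the treatment group and 376 assigned to the waitlist control group".

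Under Primary analysis, the cluster is the WeMatter group: "The clusters refer to the WeMatter groups so participants in the same WeMatter group will belong to the same cluster". The model gives it a random effect in the treated arm only, among "the random effects representing the between cluster variation in the treatment group" and the individual-level terms. The treatment effect is explained there as an average of separate block effects.

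Under Exploratory analysis, Additional specifications, the protocol then lists "more conservative estimators that include block fixed effects in the regression specification as a robustness test and include interaction terms between the treatment and blocks", so that the effect may differ between blocks. It does not say how the group random effect or the standard error of the averaged effect is handled in that model.

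**The concern.** A block fixed effect together with a fixed treatment-by-block term gives every half-block its own mean. The treated half-block is the WeMatter group. Whatever the group contributes (facilitators, peers, dynamics) goes into the fixed interaction and no longer counts as a source of error. The averaged effect is then judged only against the scatter of children within half-blocks.

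The protocol elsewhere treats group variance as real. The primary model has a term for it, and the MDES section says the treated arm has a source of variability that the control arm lacks. A check on the primary result that leaves this variance out will tend to look more precise than the primary result. If it is also labelled more conservative, a reader may take the narrower interval as added support.

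**Working it through.** **Inputs.** The MDES section gives 47 blocks of 16 (8 treated, 8 control), 376 per arm, ICC 0.01 to 0.15, R2 0.3 to 0.7, and variability of treatment effects across blocks 0 to 0.5. Table 3 gives two-sided alpha 0.05 and power 0.8.

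**1. The plan's own figures.** The protocol states no standard error for the robustness model, so the nearest check is Table 3. I used

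MDES = (t(0.975, 46) + t(0.8, 46)) × sqrt( ICC × variability / 47 + (1 − ICC)(1 − R2) / (0.25 × 16 × 47) ).

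With no attrition, columns A to F come to 0.174, 0.114, 0.161, 0.105, 0.118 and 0.198, against the stated 0.17, 0.11, 0.16, 0.11, 0.12 and 0.2. The inputs are therefore read as the protocol means them.

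**2. Aliasing.** I built the design matrix for 47 blocks, each with 8 treated and 8 control children.

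| Fixed terms | Rank | Rank after adding 47 group indicators |
|---|---|---|
| Blocks + treatment-by-block | 94 | 94 |
| Blocks + single treatment term | 48 | 94 |

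In the first row the group indicators add nothing, so the group variance cannot be estimated. In the second row it can.

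**3. Standard errors of the averaged effect** (outcome variance 1, treated-group variance equal to the ICC):

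- fixed interactions: sqrt( 2(1 − ICC)(1 − R2) / 376 )
- with group variance: sqrt( ICC / 47 + 2(1 − ICC)(1 − R2) / 376 )

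Example, ICC 0.15 and R2 0.3: 2 × 0.85 × 0.7 / 376 = 0.003165, whose root is 0.0563. Adding 0.15 / 47 = 0.003191 gives 0.006356, whose root is 0.0797. The ratio is 0.706.

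Coverage = 2Φ(t(0.975, 657) × ratio) − 1, with 752 − 94 − 1 = 657 df.

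| ICC | R2 | SE, fixed interactions | SE with group variance | Ratio | Coverage | Simulated |
|---|---|---|---|---|---|---|
| 0.01 | 0.3 | 0.0607 | 0.0624 | 0.97 | 94.4% | 95.0% |
| 0.01 | 0.7 | 0.0397 | 0.0423 | 0.94 | 93.5% | 93.2% |
| 0.15 | 0.3 | 0.0563 | 0.0797 | 0.71 | 83.4% | 83.5% |
| 0.15 | 0.7 | 0.0368 | 0.0674 | 0.55 | 71.6% | 72.0% |

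The simulation used 4,000 trials per setting, a baseline covariate and an assumed block variance of 0.05.

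**4. Column F inputs** (ICC 0.15, variability 0.5, R2 0.3). The between-group term becomes 0.15 × 0.5 / 47 = 0.001596. The standard error with it is sqrt(0.001596 + 0.003165) = 0.0690, against 0.0563. Coverage is 89.1%.

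**5. Cause and remedy.** With ICC 0, simulated coverage of the fixed-interaction interval was 95.2% (R2 0.3) and 95.7% (R2 0.7), so the loss comes from the omitted group variance. An interval for the same averaged effect with a standard error from the spread of the 47 block effects (46 df) covered 94.5% to 95.8% across all settings run.

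**The case against.** The strongest reply is that the protocol never fixes the standard error. It does not say that the interactions are fixed, that the group random effect is dropped, or that residual error is the yardstick. With random interactions, or a standard error from the between-block spread, the interval would be sound. The sentence may also list two separate checks, and the label may fit block fixed effects alone. A separate analysis plan may settle these points. This stands in part: the fault belongs to fixed interactions with a model-based standard error. That is still the plain reading of interactions placed beside block fixed effects. The aliasing follows from the layout, and the protocol itself attaches the label.

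It is also fair that, conditional on these 47 groups, the interval is valid. The primary model's random group effect and the random-effects MDES calculation aim at a wider target.

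Three stronger readings are tempting and not supported:

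- **That the primary result is compromised.** The primary model keeps the group random effect, and this model is exploratory.
- **That block fixed effects as such remove group variance.** With a single treatment term they do not (rank 48 rising to 94).
- **That coverage is badly wrong in any event.** At the protocol's lower ICC of 0.01 the loss is about 1 percentage point or less. The protocol says the level of clustering is highly uncertain, so neither end of its range can be assumed.

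**Conclusion.** The point holds for treatment-by-block terms fitted as fixed effects with a model-based standard error, judged as inference to WeMatter groups beyond the 47 in the trial. For that specification the description as more conservative is wrong: at any positive group variance the standard error is too small. Across the protocol's planning values the shortfall runs from negligible (ICC 0.01) to serious (a nominal 5% test rejects a true null about 17% of the time at ICC 0.15 and R2 0.3, and about 28% at R2 0.7).

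These sizes also assume equal residual variance in the two arms and no attrition. A smaller group variance than the ICC shrinks the effect, as the column F case shows. What is at stake is false reassurance from an exploratory check, not the validity of the primary estimate. The correction is worth making before the data are analysed.

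**What to change.** For the robustness test, specify one of the following:

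- (a) block fixed effects with a single treatment term, keeping the treated-group random effect; or
- (b) the 47 block-specific treated-minus-control differences, adjusted for Week 1 score, averaged with a standard error from their between-block spread and a t interval on 46 df.

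If treatment-by-block terms are kept to show how effects vary, take the standard error of their average from the same between-block spread. State that variance between WeMatter groups and variance of the treatment effect between blocks cannot be separated with one treated group per block. Do not describe the fixed-interaction model as more conservative.

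The cost is a change of wording and a few lines of code. Data collection, sample size and the primary analysis stay as they are.
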